3. OBJECTIVES AND ENDPOINTS

Objectives	Endpoints
Primary:	Primary:

 Part 1: To evaluate the effect of severe renal impairment on the PK of PF-06651600 following multiple oral dose administration. Part 2 (if applicable): To evaluate the effect of moderate and mild renal impairment on the PK of PF-06651600 following multiple oral dose administration. 	
 Plasma PF-06651600 PK parameters: C_{max} and AUC_{0-24}.
Secondary:	Secondary:

 To evaluate the safety and tolerability of multiple oral doses of PF-06651600 in participants with renal impairment and in healthy participants with normal renal function. 	
 Safety: treatment-emergent adverse events, clinical laboratory tests, vital signs, physical exam and ECGs.
Tertiary/Exploratory:	Tertiary/Exploratory:

 To compare additional PK parameters of PF-06651600 following administration of multiple oral doses in participants with renal impairment and in healthy participants without renal impairment. To enable exploratory research through collection of banked biospecimens, unless prohibited by local regulations or ethics committee decision. 	
 Plasma PF-06651600 PK parameters: T_{max}, AUC_{last}, CL/F, and C_{trough} on Days 8, 9, 10 and 11. Potential results from exploratory analysis of banked biospecimens (these results may or may not be generated in the context of the present study).

4. STUDY DESIGN

4.1. Overall Design

This is a Phase 1, non-randomized, open-label, multiple-dose, parallel-cohort, multisite study to investigate the effect of renal impairment on the plasma PK, safety and tolerability of PF-06651600 after multiple oral doses of 50 mg QD. A staged approach, as outlined in detail below, will be followed in the study.

Participants will be selected and categorized into normal renal function or renal impairment groups based on their estimated glomerular filtration rate (eGFR) as shown in [Table 1](#).

Table 1. Renal Function Categories by eGFR Ranges

Cohort	Renal Impairment ^a	Estimated eGFR ^b (mL/min)	Number of Participants
1	Severe Renal Impairment	<30 and not requiring dialysis	8
2	None (Normal)	≥90	8
3	Moderate Renal Impairment	≥30 to <60	8
4	Mild Renal Impairment	60 – 89	8

- a. Stages of renal impairment are based on Kidney Disease Outcomes Quality Initiative (KDOQI) Clinical Practice Guidelines for Chronic Kidney Disease (CKD).¹
- b. Estimate of eGFR based on Modification of Diet in Renal Disease (MDRD) formula. The average of the 2 screening eGFR value will be used for group assignment.
- Step 1: $eGFR \text{ (mL/min/1.73m}^2\text{)} = 175 \times (S_{cr, \text{std}})^{-1.154} \times (\text{Age})^{-0.203} \times (0.742 \text{ if female}) \times (1.212 \text{ if African American})$ where $S_{cr, \text{std}}$ denotes serum creatinine measured with a standardized assay.
 - Step 2: Convert the MDRD-derived, body surface area (BSA)-adjusted eGFR obtained above to absolute eGFR (mL/min) for eligibility assessment using the following equation:
 $eGFR \text{ (mL/min)} = eGFR \text{ (mL/min/1.73m}^2\text{)} \times \text{participant's BSA}$ where BSA is calculated as $BSA = (\text{Weight}^{0.425} \times \text{Height}^{0.725}) \times 0.007184$.

Part 1: A total of approximately 16 participants will be enrolled in Part 1; approximately 8 participants with severe renal impairment and approximately 8 with normal renal function to ensure at least 6 evaluable participants in each group. Participants from the severe renal impairment group will be recruited first. The demographics will be pooled across study sites to determine an average value for age and weight in the severe impairment group. Subsequently, the healthy participants will be recruited later such that each participant's age is within ±10 years and weight is within ±15 kg of the mean of severe renal impairment group. An attempt will be made to maintain a similar male/female ratio and racial composition between groups. Care will be taken when recruiting the healthy participants such that the entire group is not of substantially different age or of substantially different body weight than the renally impaired participants. Approval from the sponsor must be obtained **before** proceeding with dosing healthy participants with normal renal function (Cohort 2).

Participants who withdraw from the normal or severe renal impairment groups for non-safety related reasons and who are considered to be non-evaluable with respect to the primary PK objective of this study may be replaced at the discretion of the principal investigator (PI) and the sponsor to ensure at least 6 evaluable participants.

Criteria to proceed to Part 2: After statistical evaluation of results from Part 1 (see [Section 9.4](#)), Part 2 will be conducted if the point estimate of PF-06651600 area under the concentration-time curve from time 0 to 24 hours (AUC₀₋₂₄) geometric mean ratio (GMR) for the severe renal impairment group (compared to the normal group as control) is ≥2.0. If this criterion is not met, the study will stop after Part 1.

Part 2: Based on whether the decision criterion to proceed to Part 2 is met, approximately 8 participants each with moderate and mild renal impairment will be enrolled to ensure at least 6 evaluable participants in each group. As in Part 1, renal impairment classification will be based on eGFR. Healthy participants will not be enrolled in Part 2.

When recruiting the Part 2 participants, attempts to match the entire group to the participants in Part 1 with respect to age, gender and body weight will be made. Other demographics, such as race and ethnicity, may be considered for matching the Part 1 and Part 2 populations when possible.

As in Part 1, participants who withdraw from the moderate or mild impairment groups for non-safety related reasons and who are considered to be non-evaluable with respect to the primary PK objective of this study may be replaced at the discretion of the PI and the sponsor to ensure at least 6 evaluable participants.

For both Parts 1 and 2: All participants in both normal and renal impairment groups will provide informed consent and undergo Screening evaluations to determine their eligibility. Participant screening for participation in this study will consist of 2 clinical research unit (CRU) outpatient visits not more than 14 days apart (but at least 3 days apart), with the 1st screening visit occurring within 28 days prior to administration of IP. Each participant will be admitted to the research unit on Day -1 (at least 12 hours prior to the dosing of PF-06651600 on Day 1). An eGFR value for group placement (provided stable renal function is still demonstrated) will be obtained by the average of the 2 screening values (using the Modification of Diet in Renal Disease [MDRD] equation). If the renal function stability criterion is met but the renal function classification category changes between Screening Visit 1 (S1) eGFR and the average of the S1 and Screening Visit 2 (S2) eGFRs, the eGFR measurement at Day -1 will also be used to determine the appropriate group classification category using an average of all 3 eGFR values, to determine whether the participant will be eligible for enrollment.

Eligible participants will be admitted to the CRU on Day -1 and will be confined in the CRU until Day 11. If participant meets all screening criteria at S2 visit, and Day -1 visit can be performed immediately, the participant may be admitted to the unit at conclusion of S2 visit.

Starting on Day 1, participants will receive a 50 mg QD dose of PF-06651600 up to Day 9. On the morning of Day 10, the participants will receive a 50 mg QD dose of PF-06651600 after a fast of at least 10 hours. No food will be allowed for at least 4 hours post-dose. Predose PK samples will be collected on Days 8, 9 and 10 for assessment of C_{trough} . Postdose serial blood and urine samples at specified intervals (as per [Schedule of Activities](#)) will be collected on Day 10 for 24 hours for plasma and urine PK assessments, prior to discharge from the CRU on Day 11. The eGFR value will be determined on Day -1, 2, 5, 8, and 11, and the average eGFR values from Day -1 to Day 11 will be used in PK analysis.

Safety assessments (as specified in the [Schedule of Activities](#)) will be performed during screening, prior to dosing on Day -1, Day 5 and Day 11. Only serum creatinine will be additionally assessed on S2, Day 2, and Day 8 for eGFR estimation. Physical examinations, vital sign measurements, and clinical laboratory tests will be conducted and AEs will be monitored as per [Schedule of Activities](#) to assess safety. The total participation time (ie, CRU confinement time for study procedures) for each participant in this study is approximately 11 nights/12 days (excluding screening & Follow-Up contact). Participants will have a follow-up phone call 28-35 days after last dose administration to assess for AEs.

All procedures and their timelines follow the [Schedule of Activities](#).

Age/Weight/Gender Matching Criteria:

Part 1: Participants with severe renal impairment will be enrolled first and their demographics will be pooled across study sites. Enrollment of age-, weight-, and gender-matched healthy participants (normal renal function group) will begin after the severe renal impairment participants have completed the in-patient portion of the study. Demographics of the healthy participants will be matched to the demographics of the severe renal impairment group such that the mean body weight for the healthy group is within ± 15 kg of the mean body weight of the participants with renal impairment and mean age is within ± 10 years of the mean age of the participants with renal impairment. In general, care should be taken when recruiting the healthy participants such that the entire group is as closely matched in age and body weight to the impairment participants as possible. An attempt will be made to maintain a similar male/female ratio and racial composition of the cohorts.

Part 2: Healthy participants will not be enrolled in this part. Healthy participants from Part 1 will be used as the control group for the moderate and mild impairment participants. Statistical considerations to account for any differences in demographics are detailed in [Section 9.4](#).

Calculation of eGFR:

The following MDRD equation will be used to calculate eGFR ($S_{cr, std}$ denotes serum creatinine measured with a standardized assay for serum creatinine):

$$\text{eGFR (mL/min/1.73m}^2\text{)} = 175 \times (S_{cr, std})^{-1.154} \times (\text{Age})^{-0.203} \times (0.742 \text{ if female}) \\ \times (1.212 \text{ if African American})$$

Note that the value of eGFR, which is directly obtained from the lab or calculated using the equation above, is generally normalized to an average body size of 1.73 m^2 for diagnosis, prognosis and treatment of renal disease. In terms of clearance of renally filtered drugs (including secreted drugs), renal elimination capacity is related to absolute glomerular filtration rate (GFR) in mL/min. To use the MDRD-derived, body surface area (BSA)-adjusted value of eGFR to obtain absolute glomerular filtration rate (GFR) (mL/min)

for renal disease classification or participant assignment into different renal disease groups, this value should be multiplied by the individual participant's BSA (ie, measured BSA/1.73 m²). The BSA of an individual can be calculated by the following formula as described below:

$$BSA = (Weight^{0.425} \times Height^{0.725}) \times 0.007184$$

In summary, GFR in mL/min calculated as below will be used for renal impairment group placement:

Step 1: Obtain the MDRD-derived eGFR:

- eGFR (mL/min/1.73m²) = 175 × (S_{cr, std})^{-1.154} × (Age)^{-0.203} × (0.742 if female) × (1.212 if African American) where S_{cr, std} denotes serum creatinine measured with a standardized assay.

Step 2: Convert the MDRD-derived, BSA-adjusted eGFR obtained above to absolute GFR (mL/min) for eligibility assessment using the following equation:

- **eGFR (mL/min)** = eGFR (mL/min/1.73m²) × participant's BSA where BSA is calculated as $BSA = (Weight^{0.425} \times Height^{0.725}) \times 0.007184$.

CL_{CR} will also be estimated from a spot serum creatinine measurement using the following Cockcroft-Gault (C-G) equation:

$$CL_{CR} \text{ (mL/min)} = \frac{[140 - \text{age (years)}] \times \text{total body weight (kg)} \times (0.85 \text{ for females})}{72 \times \text{serum creatinine (mg/dL)}}$$

Note that eGFR calculated by the MDRD equation will be used for categorization of degrees of renal impairment. Nevertheless, renal function will be estimated using both C-G and MDRD equations in this study and dose recommendations will be made using both C-G and MDRD equations.

To be enrolled into the study, participant should demonstrate stable renal function, with ≤25% change based upon screening S1 eGFR and screening S2 eGFR (calculated by the MDRD equation). The S2 eGFR assessment should be performed between 3 to 14 days after the S1 eGFR assessment. The average of these 2 eGFR values will be used for group placement based on the renal function classification category.

- If the renal function stability criterion is met and the renal function classification category remains the same between S1 eGFR and the average of the S1 and S2 eGFRs, participant will be eligible for enrollment.
- If the renal function stability criterion is not met, participant will be screen failed.

- If the renal function stability criterion is met but the renal function classification category changes between S1 eGFR and the average of the S1 and S2 eGFRs, the eGFR measurement at Day -1 will also be used to determine the appropriate group classification category using an average of all 3 eGFR values, to determine whether the participant will be eligible for enrollment.

In case of screen failure related to eGFR stability and/or change in the renal function classification category, participant may be re-screened once after a 30-day period, provided that the initial screen failure is not due to an Inclusion/Exclusion criterion that results in permanent disqualification from enrollment (eg, medical history). This can be done only with Sponsor's approval.

Please see Table 2 below regarding demonstration of stable renal function:

Table 2. Criteria to Establish Stable Renal Function

Renal function Measurement	eGFR (mL/min)	Criterion for stability
S1	G1	
S2 (Within 3 to 14 days after S1)	G2	$\Delta = G2 - G1 \times 100 / G1^a$ If $\Delta \leq 25\%$; stable If $\Delta > 25\%$; not stable

Abbreviations: S1= Screening Visit 1; S2= Screening Visit 2.

a. Parenthesis of || represents absolute values.

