**For both Parts 1 and 2:** All participants in both normal and renal impairment groups will provide informed consent and undergo Screening evaluations to determine their eligibility. Participant screening for participation in this study will consist of 2 clinical research unit (CRU) outpatient visits not more than 14 days apart (but at least 3 days apart), with the 1st Screening visit occurring within 28 days prior to administration of IP. Each participant will be admitted to the research unit on Day -1 (at least 12 hours prior to the dosing of PF-06651600 on Day 1). An eGFR value for group placement (provided stable renal function is still demonstrated) will be obtained by the average of the 2 screening values (using the Modification of Diet in Renal Disease [MDRD] equation). If the renal function stability criterion is met but the renal function classification category changes between Screening Visit 1 (S1) eGFR and the average of the S1 and Screening Visit 2 (S2) eGFRs, the eGFR measurement at Day -1 will also be used to determine the appropriate group classification category using an average of all 3 eGFR values, to determine whether the participant will be eligible for enrollment.

**Calculation of eGFR:** The following MDRD equation will be used to calculate eGFR (*Scr*, *std* denotes serum creatinine measured with a standardized assay for serum creatinine):

$$eGFR \text{ (mL/min/1.73 m}^2\text{)} = 175 \times (\text{Scr}_{\text{cr, std}})^{-1.154} \times (\text{Age})^{-0.203} \times (0.742 \text{ if female}) \\ \times (1.212 \text{ if African American})$$

Note that the value of eGFR, which is directly obtained from the lab or calculated using the equation above, is generally normalized to an average body size of 1.73 m^2 for diagnosis, prognosis and treatment of renal disease. In terms of clearance of renally filtered drugs (including secreted drugs), renal elimination capacity is related to absolute glomerular filtration rate (GFR) in mL/min. To use the MDRD-derived, body surface area (BSA)-adjusted value of eGFR to obtain absolute glomerular filtration rate (GFR) (mL/min) for renal disease classification or participant assignment into different renal disease groups, this value should be multiplied by the individual participant's BSA (ie, measured BSA/1.73 m^2). The BSA of an individual can be calculated by the following formula as described below:

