$$BSA = (\text{Weight}^{0.425} \times \text{Height}^{0.725}) \times 0.007184$$

In summary, GFR in mL/min calculated as below will be used for renal impairment group placement:

Step 1: Obtain the MDRD-derived eGFR:

$eGFR \text{ (mL/min/1.73 m}^2\text{)} = 175 \times (\text{Scr}_{\text{cr, std}})^{-1.154} \times (\text{Age})^{-0.203} \times (0.742 \text{ if female}) \times (1.212 \text{ if African American})$  where *Scr*, *std* denotes serum creatinine measured with a standardized assay.

Step 2: Convert the MDRD-derived, BSA-adjusted eGFR obtained above to absolute GFR (mL/min) for eligibility assessment using the following equation:

$eGFR \text{ (mL/min)} = eGFR \text{ (mL/min/1.73 m}^2\text{)} \times \text{participant's BSA}$  where BSA is calculated as  $BSA = (\text{Weight}^{0.425} \times \text{Height}^{0.725}) \times 0.007184$ .

CLCR will also be estimated from a spot serum creatinine measurement using the following Cockcroft-Gault (C-G) equation:

$$CL_{\text{CR}} \text{ (mL/min)} = \frac{[140 - \text{age (years)}] \times \text{total body weight (kg)} \times (0.85 \text{ for females})}{72 \times \text{serum creatinine (mg/dL)}}$$

Note that eGFR calculated by the MDRD equation will be used for categorization of degrees of renal impairment. Nevertheless, renal function will be estimated using both C-G and MDRD equations in this study and dose recommendations will be made using both C-G and MDRD equations.

To be enrolled into the study, participant should demonstrate stable renal function, with  $\leq 25\%$  change based upon screening S1 eGFR and screening S2 eGFR (calculated by the MDRD equation). The S2 eGFR assessment should be performed between 3 to 14 days after the S1 eGFR assessment. The average of these 2 eGFR values will be used for group placement based on the renal function classification category.

If the renal function stability criterion is met and the renal function classification category remains the same between S1 eGFR and the average of the S1 and S2 eGFRs, participant will be eligible for enrollment.

If the renal function stability criterion is not met, participant will be screen failed.

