### **5.5. Treatment/Group Misallocations**

All analyses will be performed on an “as-treated” basis and will not include data from subjects who are randomized but not treated.

If based on eGFR value(s) a subject is assigned to the wrong renal impairment group, this subject will be reassigned to the correct group and analyzed for safety and PK analysis according to his reassigned group.

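### Step 2 of the eGFR conversion leaves out the division by 1.73; used as printed, it moves the 30/60/90 mL/min group cut-offs to true values of 17.3/34.7/52.0

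*Protocol*

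**What the plan says.** Groups are defined on absolute eGFR in mL/min: severe <30, moderate ≥30 to <60, mild 60–89, normal ≥90 (Table 1 in both documents). The value is built in two steps. Step 1 is the MDRD equation, which returns mL/min per 1.73 m². Step 2 converts this to mL/min.

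The explanatory paragraph under Calculation of eGFR (Protocol 4.1) gives the Step 2 multiplier as "BSA (ie, measured BSA/1.73 m²". SAP 2.1 repeats it: "this value should be multiplied by the individual participant's BSA (ie, measured BSA/1.73".

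The Step 2 equation does not follow that paragraph. In Protocol 4.1 it reads "eGFR (mL/min/1.73m²) × participant's BSA where BSA is calculated as" Weight^0.425 × Height^0.725 × 0.007184, which is the whole surface area in m². The same equation stands in the protocol's Table 1 footnote b, SAP Table 1 footnote b and SAP 2.1. It is the version presented as operative: "In summary, GFR in mL/min calculated as below will be used for renal impairment group placement". Table 1 footnote b introduces it with "Convert the MDRD-derived, body surface area (BSA)-adjusted eGFR obtained above to absolute eGFR (mL/min) for eligibility assessment using the following equation", and SAP 2.1 with "Convert the MDRD-derived, BSA-adjusted eGFR obtained above to absolute GFR (mL/min) for eligibility assessment using the following equation".

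SAP 5.5 provides a correction: "If based on eGFR value(s) a subject is assigned to the wrong renal impairment group, this subject will be reassigned to the correct group".

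**The concern.** A site or programmer looking for the placement equation will find Step 2 and multiply two numbers. Done that way, the result is too high by a constant factor and participants can land in the wrong cohort.

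The grouping carries the whole study. Renal group is the only factor in the one-way ANOVA (SAP 8.1 and Appendix 1). The severe/normal comparison alone decides whether the study continues: "Part 2 will be conducted if the point estimate of PF-06651600 area under the concentration-time curve from time 0 to 24 hours" has a severe/normal geometric mean ratio of at least 2.0. Protocol 4.1 also says dose recommendations will use MDRD alongside Cockcroft-Gault.

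The SAP's safeguard may not help. The SAP carries the same Step 2, so a reassignment check programmed from it would confirm the wrong group. The 25% stability test cannot reveal the error either, because a constant factor cancels in a ratio.

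**Working it through.** The plan states no derived figure to reproduce; the cut-offs are design inputs. The check is unit algebra followed by one worked participant.

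**Factor.** Let E be the MDRD value in mL/min/1.73 m².
- Explanatory text: E × BSA/1.73
- Step 2 as printed: E × BSA
- Ratio: 1.73 for every participant, whatever the BSA

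A cut-off c applied to the printed value is therefore a true absolute cut-off of c/1.73: 30/1.73 = 17.34, 60/1.73 = 34.68, 90/1.73 = 52.02. The upper limit of the mild band becomes 89/1.73 = 51.45.

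**Classification by true absolute eGFR (mL/min), if Step 2 is used as printed.**

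| True value | Intended group | Group by printed Step 2 |
|---|---|---|
| <17.3 | severe | severe |
| 17.3 to <30 | severe | moderate (not open in Part 1) |
| 30 to <34.7 | moderate | moderate |
| 34.7 to <52 | moderate | mild |
| 52 to <60 | moderate | normal |
| 60 to <90 | mild | normal |
| ≥90 | normal | normal |

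Table 1 ends mild at 89, so printed values between 89 and 90 (true 51.45 to 52.02) strictly fall in no group. This is immaterial here.

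**Worked participant.** The profile is assumed for illustration: a man aged 60, 80 kg, 170 cm, without the 1.212 race factor.
- BSA = 0.007184 × 80^0.425 × 170^0.725 = 1.915 m²; BSA/1.73 = 1.107
- E = 175 × Scr^−1.154 × 60^−0.203

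| Creatinine (mg/dL) | E | With divisor, E × 1.107 | As printed, E × 1.915 |
|---|---|---|---|
| 4.5 | 13.44 | 14.9 severe | 25.7 severe |
| 2.5 | 26.48 | 29.3 severe | 50.7 moderate |
| 2.2 | 30.68 | 34.0 moderate | 58.8 moderate |
| 1.0 | 76.22 | 84.4 mild | 146.0 normal |

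Solving for creatinine, he crosses 30/60/90 mL/min at 2.45/1.34/0.95 mg/dL with the divisor and at 3.94/2.16/1.52 mg/dL as printed.

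**Effect on the severe/normal ratio.** A reference group opened to true values of 52 to <90 would, if exposure rises as renal function falls, pull the ratio towards 1. A severe group restricted to <17.3 would push it away from 1. The documents do not determine the net direction.

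**Effect on the Part 2 regression.** With 1.73x in place of x as the regressor, the slope becomes 1/1.73 = 0.578 of its value; intercept and R² do not change. This applies if the regressor is this eGFR. The example code in SAP Appendix 1 names it clcr, and if that means Cockcroft-Gault clearance, the regression is unaffected.

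**The case against.** **The intent can be recovered.** The paragraph just before Step 2 supplies the divisor, and converting mL/min/1.73 m² to mL/min requires it. Much SAP text is copied from the protocol, so the four occurrences are probably one slip repeated. Nothing shows that anyone used the printed form. All of this stands, and it makes the correction easy. It does not make the placement equation right, because Step 2 defines BSA numerically and says to multiply by it.

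**Other data could expose the error.** Cockcroft-Gault clearance is also calculated. For the man above it is 35.6 at creatinine 2.5 and 88.9 at 1.0, well below the printed 50.7 and 146.0. A careful reader might notice, but neither document requires the comparison.

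**Cohort 2 has other entry criteria.** Protocol 5.1.2 requires no clinically relevant abnormality, laboratory tests included, and 5.2.2 excludes clinically significant renal disease. These would keep out many participants with true values near 52. They rest on judgement and may not stop values of 60–89.

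**The effect on exposure may be small.** Unchanged urinary excretion is below 8% of dose (Protocol 2.1). If that approximates the renal share of clearance (an assumption), a reference group at true 60 rather than 90 shifts AUC by about 1/(1 − 0.08/3) = 1.03, and total loss of renal clearance by 1/0.92 = 1.09. Protocol 4.2 expects little effect on CYP enzymes. This bounds the renal part only. Protocol 2.1 justifies the study by possible effects on non-renal pathways, which are not quantified.

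**Re-derivation has practical limits.** Screen-failure data stay at source (Protocol 5.4), and SAP 5.5 can reassign only people who were enrolled. This stands and is reflected in the remedy.

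**Conclusion.** The point holds and must be fixed. Both documents contradict themselves on the equation that assigns renal group, and the version presented as operative is the wrong one. The contradiction and the 1.73-fold factor need no assumption. The misclassification depends on Step 2 having been used as printed, which the documents neither show nor exclude. In that case the severe cohort represents only true eGFR below 17.3 mL/min, participants with true values of 17.3 to <30 fail its entry criterion, and the normal eGFR criterion admits true values from 52 mL/min. No claim is made that the 2.0 trigger would be crossed or missed as a result.

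**What to change.** 1. In the protocol's Table 1 footnote b, Protocol 4.1 Step 2, SAP Table 1 footnote b and SAP 2.1 Step 2, write: eGFR (mL/min) = eGFR (mL/min/1.73 m²) × (participant's BSA / 1.73).
2. Confirm and document which version sites and programmers used for placement.
3. Only if the printed version was used, re-derive the S1, S2 and (where used) Day -1 values for everyone screened, working from site source records for screen failures. Reassign enrolled participants under SAP 5.5 with the corrected equation.
4. State how a cohort left with fewer than 6 evaluable participants would be refilled. Protocol 4.1 provides replacement only for participants who withdraw.

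Items 1 and 2 cost a short amendment or clarification, a SAP edit and one check of the implemented calculation. Items 3 and 4 are a real further cost, but arise only if the printed version was used. Cohort 1 would lose no one, since anyone placed there has a true value below 17.3, but it would not represent 17.3 to <30. Cohort 2 would lose anyone with a true value of 52 to <90, and cohorts might need refilling.
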